#### **3.10.1 Primary Efficacy Analysis - Complete Clearance of All Warts**

The primary efficacy summary will tabulate the number and percent of subjects achieve complete clearance (PWA=0) at each analysis visit by treatment group. This analysis will also be done by treatment group and treatment cycle. Treatment cycle start date can vary from subject to subject so analysis visits will be derived from period study day as

described in [Appendix A](#) and [Section 3.3](#). All efficacy analyses will be descriptive and there will be no formal statistical test to compare treatment groups.

Any identified common wart for a subject that has missing PWA data will be treated as not clear for the purpose of the primary efficacy analysis. A sensitivity analysis will be carried out using observed data.

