6. STUDY DESIGN

This is a phase 3, open label, long term safety study of A-101 Topical Solution 45% in subjects with common warts.

In order to be eligible for A-101-WART-303, subjects must have completed protocol treatment on either the A-101-WART-301 or A-101-WART-302 study.

Subjects that have complete clearance of all warts at the end of A-101-WART-301 or A-101-WART 302 may enter into the A-101-WART-303 study following completion of the Visit 1 assessments. These subjects will be followed every 6 weeks to assess for a recurrence or development of new common warts. If a recurrence occurs or a new wart develops these subjects may return to the investigational site to receive A-101 Topical Solution 45% twice a week for an additional 8 weeks.

Subjects that have warts that have not cleared (or were not treated) at the completion of A-101-WART-301 or A-101-WART 302 may enter into the A-101-WART-303 study following completion of the Visit 1 assessments will receive A-101 Topical Solution 45% twice a week for 8 weeks. Subjects may continue to receive A-101 Topical Solution 45% twice a week for 8 weeks if their warts are not clear at the end of the 8-week treatment period but the 8 weekly treatments must be initiated by Day 122.

Visit 1 of A-101-WART-303 can be the same day as Visit 13 of either A-101-WART-301 or A-101-WART 302.

All subjects will be required to remain on study for a total of 6 months.

During the study, the investigator may identify from 1 to 6 common warts (during a 8 week treatment period) to be treated twice a week for up to 8 weeks (maximum of 16 treatment applications). An 8-week treatment course may be repeated.

Refer to **Table 2** and **Table 3** and for a complete list of protocol required study assessments.

8-week treatment period may be initiated anytime from Day 1 to Day 122

[figure not shown]

Figure 1 WART 303 Study Diagram for Treatment

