11.3. Prohibited Therapies

During the course of this study, subjects are prohibited from using the following treatment therapies to treat the identified common warts:

- Intralesional Therapy
 - Immunotherapy (e.g., *Candida* antigen, mumps antigen, *Trichophyton* antigen)
 - Anti-metabolite therapy (e.g., bleomycin, 5-fluorouracil);
- Systemic Therapy
 - Immunomodulatory/immunosuppressant therapy (e.g., etanercept, alefacept, infliximab);
 - Glucocortico-steroids (inhaled and intra-nasal steroids are permitted);
- Topical Therapy
 - LASER (e.g., pulsed-dye laser [PDL], light (e.g., intense pulsed light [IPL], photodynamic therapy [PDT], other energy-based therapy);
 - Immuno-therapy (e.g., imiquimod, squaric acid dibutyl ester [SADBE], etc.);
 - Anti-metabolite therapy (e.g., 5-fluorouracil);
 - Retinoids;
 - Liquid nitrogen, electrodesiccation, curettage;
 - Over-the-counter (OTC) wart therapies and cantharidin.

The investigator should notify the Medical Monitor immediately if any prohibited therapies are required to ensure subject safety.

For subjects starting an 8-week treatment schedule for an identified wart, topical products (e.g., moisturizers, sunscreens, etc.) must not be applied to any of their identified common warts **within 12 hours prior** to any treatment application (Note: routine cleansing products are allowed).

After the completion of a treatment application, subjects must **NOT wash/submerge** the treated common wart for at least **6 hours** and must not apply any topical products to the treated common wart for at least **6 hours**. Parents/legal guardians of children must ensure that the child does not put the treated area in their mouth, or eyes, until completely dry after the application. If the treated area is not completely dry 10 minutes after the application, the area should be blotted dry.

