### **3.8 Prior and Concomitant Medications, Therapies and Procedures**

Prior and concomitant medications are listed only. The period(s) (prior, on treatment, and post-therapy) in which the medications were administered will be flagged. These rules are explained in Data Handling and Programming Specification Document in detail. Medications are coded using the WHO Drug (March 2019).

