### **3.9 Protocol Violations**

Protocol violations will be identified prior to database lock to measure adherence to key aspects of the protocol (see Section 15 of the protocol for full definitions). Specific data fields that will be examined to identify protocol violations include inclusion/exclusion criteria and prohibited prior and concomitant medications as well as all deviations identified by the investigator. All protocol violations will be listed.

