### **3.10 Efficacy Endpoints**

The primary and secondary efficacy analyses will be carried out on the Safety Population. Efficacy summaries will be supported by listings.

Primary Efficacy Endpoint: Proportion of subjects who achieve complete clearance (PWA=0) of all identified warts at each analysis visit window by treatment group and treatment cycle.

Four secondary efficacy endpoints are:

- Durability of response: For subjects with all warts achieving a status of Clear (PWA=0), the number of weeks all warts remain clear by treatment group and treatment cycle.
- Mean per-subject percent of treated warts that are Clear (PWA=0) at each analysis visit by treatment group and treatment cycle.
- Proportion of subjects with a single wart at baseline whose wart is Clear (PWA=0) by analysis visit, treatment group, and treatment cycle.
- Median time to achieve onset of Clearance (PWA=0) for all treated warts by treatment group and treatment cycle.

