### 3.10.2 Secondary Efficacy Analyses

#### 3.10.2.1 Durability of Response

Difference in time to recurrence of wart by treatment group is summarized using Kaplan Meier analysis. This analysis will be done at overall study level and by treatment cycle.

- **Overall Study Level:** Time to recurrence will be presented graphically with a Kaplan Meier curve. For this analysis, time to first recurrence in the study will only be included for each subject. Subjects with no wart at the end of study will be censored. The proportion of subjects that remain clear of warts at the end of the study will also be presented.
- **By Treatment Cycle:** For this analysis, time to first recurrence in the treatment cycle will only be included for each subject. Subjects with no wart at the end of the treatment cycle will be censored.

Kaplan-Meier estimates and associated confidence intervals are obtained using SAS statements consistent with the following syntax:

```
PROC LIFETEST ALPHA=.05;  
  TIME DAYS*CENSOR(1);  
  SURVIVAL OUT=SURV CONFTYPE=LOGLOG;  
  STRATA TREATMENT GROUP;
```

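### The SAP has no rule for identified warts treated with a prohibited local wart therapy, so a later PWA=0 counts as an A-101 clearance

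*SAP*

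**What the plan says.** SAP 3.10 sets the primary efficacy endpoint as "Proportion of subjects who achieve complete clearance (PWA=0) of all identified warts at each analysis visit window by treatment group and treatment cycle", and 3.10.1 will "tabulate the number and percent of subjects achieve complete clearance (PWA=0) at each analysis visit by treatment group". The only non-response rule there concerns missing data: "Any identified common wart for a subject that has missing PWA data will be treated as not clear". One sensitivity analysis, on observed data, goes with it. The secondary analyses (3.10.2.1 to 3.10.2.4) rest on PWA=0 or on wart recurrence. For durability at study level, "Subjects with no wart at the end of study will be censored".

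Protocol 11.3 bars a list of therapies on the identified warts during the study. The local ones are liquid nitrogen, electrodesiccation, curettage, laser and light, topical or intralesional immunotherapy and antimetabolites, retinoids, cantharidin and OTC wart products. Its one instruction on their use is "The investigator should notify the Medical Monitor immediately if any prohibited therapies are required to ensure subject safety". Protocol 15.2 makes giving a prohibited medication a protocol violation, recorded on the CRF.

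In the analysis this information goes only to listings. SAP 3.8 says "Prior and concomitant medications are listed only" and SAP 3.9 says "All protocol violations will be listed". Efficacy is analysed in the Safety population, which is everyone with at least one application (SAP 3.1). There is no per-protocol set.

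**The concern.** The barred local therapies are used to remove warts. The protocol itself treats them as confounders: exclusion 7 requires a washout where they would interfere with treatment or assessment, for example 60 days for liquid nitrogen and curettage and 28 days for OTC products. Yet once the study is running, a wart frozen with liquid nitrogen and then scored PWA=0 enters the tables exactly like one cleared by A-101. The plan is strict about a missing PWA, which it scores as not clear, and silent about a PWA=0 that another treatment may explain.

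The effect runs one way. With a single open-label arm there is no concurrent control in which similar use would show up, and the observed-data analysis only changes how missing scores are handled. At stake are the primary efficacy summary and duration of response, which is a named secondary objective.

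**Working it through.** **1. The plan's own figure.** SAP 3.13 and protocol 14.1 give 400 subjects, 200 of them previously on active treatment, and 26% of warts clear at the end of the parent studies. 200 x (1 - 0.26) = 148, which matches the stated 148. The point does not depend on this figure; it only supplies a scale.

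**2. The efficacy rules, read for other wart therapy.**
- 3.10.1, complete clearance: PWA=0 counts; a missing PWA is not clear; other therapy is not mentioned.
- 3.10.2.1, durability: first recurrence is the event; no wart at the end of the study or cycle is censored; other therapy is neither an event nor a censoring point.
- 3.10.2.2, percent of warts cleared: non-missing PWA only; other therapy is not mentioned.
- 3.10.2.3, single-wart clearance: a missing assessment is non-clearance; other therapy is not mentioned.
- 3.10.2.4, time to clearance: subjects not cleared at the end of a cycle are censored; other therapy is not mentioned.

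Protocol 14.3 has no such rule either.

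**3. Where the exposure lies.** PWA is scheduled on Days 1, 29, 60 and 182 (protocol 9.2 and Table 2). For a subject who starts no new course, 182 - 60 = 122 days pass without a scheduled PWA, or 122/182 = 67% of the study. The Table 2 calls on Days 102 and 144 cover safety, concomitant medication and new warts, but do not ask whether a cleared wart has come back. The Table 3 calls, for subjects under observation, do ask. No course may start after Day 122, so a subject not then in a course has up to 182 - 122 = 60 days without access to study treatment.

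That is the worst case. With courses starting on Days 1, 60 and 119, and the last application on course Day 53, the final application falls on Day 119 + 52 = 171, which is 11 days before Day 182.

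**4. Clearance, illustration.** Let p be clearance due to A-101, q the share of uncleared subjects who use a barred local therapy, and c the share of those users who then score clear. The reported rate is p + (1 - p) x q x c. Take p = 26% as a placeholder; q and c are assumptions.
- q = 5%, c = 50%: 0.74 x 0.05 x 0.5 = 1.9 points (2.7 of 148 subjects).
- q = 15%, c = 50%: 0.74 x 0.15 x 0.5 = 5.6 points (8.2 of 148).
- Wider range, from q = 2%, c = 25% to q = 20%, c = 75%: 0.4 to 11.1 points.

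With the rule proposed below, each of these would read 26%.

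**5. Durability, illustration.** If a share R of subjects truly recur and a fraction m of those recurrences is treated elsewhere before being scored, the reported share remaining clear is 1 - R x (1 - m). With R = 40% and m = 5% to 20%, it reads 62% to 68% instead of 60%. With R = 20%, it reads 81% to 84% instead of 80%. R and m are assumptions.

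**The case against.** Much can be said on the other side, and part of it stands.

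- **A recorded recurrence is already handled.** A reader might infer that a wart which recurs on Day 90, is treated with an OTC product and is absent at the end of the study is censored as still clear. SAP 3.10.2.1 does not support that if the recurrence was recorded: it uses the first recurrence, and later absence does not undo it. The durability problem is limited to recurrences treated elsewhere without being scored. If the other therapy is also never reported, no analysis rule can recover the case.
- **Subjects are not left unobserved.** Repeat courses are allowed, up to three cycles (SAP 3.3). Calls on Days 102 and 144 collect concomitant therapies. Table 3 subjects are told to contact the site as soon as they suspect a wart. The 60-day interval is therefore not typical of all subjects.
- **Not every output is exposed alike.** A therapy used on Day 130 cannot alter the Day 29 or Day 60 rows. Time to clearance is touched only by use within the cycle: if a cycle means the 8-week course, late use does not reach it.
- **The protocol does not condone such use.** A reader might take 11.3, together with "All subjects will be required to remain on study for a total of 6 months", to mean that users are expected and kept on study. The first sentence concerns therapies needed for subject safety and the second is a general statement of duration. Protocol 7.3 allows removal from study therapy for changed compliance with entry criteria. That removal is discretionary, however, and does not change a PWA already scored.
- **A separate data-handling document exists.** It was not supplied. The SAP cites it for medication periods, safety data handling and date imputation, not for efficacy response. The sponsor can confirm that it holds no such rule.
- **The stakes are modest.** The primary objective is safety, efficacy is descriptive with no test, and affected subjects will be visible in listings.

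None of this supplies the missing rule. A listing lets a reader find affected subjects but leaves the reported rates as they are.

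**Conclusion.** The gap is real and its direction is certain. As the SAP stands, a PWA=0 after a barred local therapy on an identified wart counts as clearance, and a recurrence treated elsewhere before it is scored is censored as clear. The main exposure is in visits after the 8-week course, above all the end-of-study row, and in durability.

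The size is not known. The 2 to 6 points rest on assumed use of 5-15% and on half of users clearing. The 26% is a wart-level assumption for the parent studies, borrowed here as a subject-level placeholder. A reader might turn this into a relative inflation of 7% to 21% (1.85/26 to 5.55/26), but the documents do not support quoting that as an estimate. The consequence is overstated descriptive rates in a safety study, not a false-positive test. The correction is worth making before database lock, so that the choice is not made after the data are seen.

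**What to change.** Add to SAP 3.10, for the local wart-directed therapies in protocol 11.3:

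- From the date such a therapy is used on an identified wart, score that wart as not clear at later visits in 3.10.1, 3.10.2.2 and 3.10.2.3, and do not count it as a clearance event in 3.10.2.4.
- In 3.10.2.1, count such use on a previously cleared wart as a recurrence on that date, with censoring at that date as a sensitivity analysis.
- Keep the PWA-as-observed tables as a sensitivity analysis.
- Report the number of subjects affected, by treatment group and cycle.
- Record the wart number with the concomitant therapy.

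Do not extend the rule to systemic therapies given for other conditions. Protocol 11.3 also names systemic glucocorticosteroids, and a steroid course for an unrelated illness should not turn every cleared wart into a recurrence.

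The cost is SAP wording and one field on the concomitant-therapy CRF. New therapies are already recorded (protocol 11.2) and prohibited medications are already reviewed before lock (SAP 3.9). The downside is slightly lower clearance and durability figures.

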9.2. Common Wart Dimensions and Physician's Wart Assessment (PWA)

Each identified wart that will be treated with A-101 study medication will be measured using the Aclaris supplied ruler. The longest axis of each identified wart will be documented on the subject's eCRF.

The Physician's Wart Assessment (PWA) is the Investigator's assessment of the severity of each identified common wart at a particular time-point. The Investigator should NOT refer to any other assessments to assist with this evaluation. This evaluation IS NOT a comparison with the PWA performed at any other visit.

During an 8-week treatment period, subjects will have their identified warts assessed using the PWA at the following time-points: Day 1, Day 29, Day 60 and Day 182.

The Investigator will assess each identified common wart and report the one integer that best describes the common wart severity using the following scale.

Physician's Wart Assessment	
Grade	Descriptor
0	Clear: No visible wart. No further treatment is indicated
1	Near Clear: a visible wart that is less than 3 mm in maximal diameter (or length)
2	A visible wart \geq 3 mm and $<$ 6 mm in maximal diameter (or length)
3	A visible wart \geq 6 mm in maximal diameter (or length)

The physician is encouraged to use a ruler or caliper and to feel the wart or skin area to help his/her assessment.

Common warts that are assessed by the investigator as having cleared (PWA =0) will be instructed not to continue to apply the A-101 study medication.

Refer to [Appendix 2](#) for the PWA Site Manual.

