**Table 2: Study Procedures for Subjects with Common Warts at Visit 1**

Visit	V1	V2	V3	V4	V5	V6	V7	V8
Visit Day	Day 1	Day 15	Day 29	Day 43	Day 60	Day 102	Day 144	Day 182
Visit Windows		+3 Days	+ 3 Days	+ 3 Days	+ 3 Days	+ 3 Days	+ 3 Days	+ 2 Days
In Office Visit	▲ 		▲		▲			▲
Phone Call		▲ 		▲ 		▲ 	▲ 	
Informed Consent	▲							
Inclusion Criteria/Exclusion Criteria	▲							
Clinical Chem / CBC 								▲
Common Wart Identification	▲ 							
Common Wart Dimensions	▲		▲		▲			▲
Physician's Wart Assessment	▲		▲		▲			▲
Local Skin Reactions	▲		▲		▲			▲

Visit	V1	V2	V3	V4	V5	V6	V7	V8
Study Medication Application	▲	▲	▲	▲				
Study Medication Dispensing and Instructions for at home application	▲		▲		▲			
Concomitant therapies		▲	▲	▲	▲	▲	▲	▲
Adverse Events	▲	▲	▲	▲	▲	▲	▲	▲

 Visit 1 of A-101-WART 303 may occur on the same day as Visit 13 of A-101-WART 301 or A-101-WART 302.

 Subjects who do not have their Visit 1 assessment on Visit 13 of A-101-WART 301 or A-101-WART-302 will have to have a clinical chemistry and a complete blood count drawn and sent to the central laboratory for analysis. A complete blood count (including hematocrit, hemoglobin, platelet count, red blood cell count and morphology, white blood cell count and differential (absolute and %) including basophils, eosinophils, lymphocytes, monocytes and neutrophils and a clinical chemistry panel including albumin, alkaline phosphatase, alanine aminotransferase (ALT), aspartate aminotransferase (AST), blood urea nitrogen (BUN), bicarbonate, calcium, chloride, creatinine, glucose, lactate dehydrogenase (LDH), phosphorus, potassium, sodium, total bilirubin, total protein, and uric acid.

 Warts that are identified for treatment must meet the requirements as outlined in Section 9.1.

 Investigational site staff will be required to make a phone contact with the subject on Day 15, Day 43, Day 102 and Day 144 to assess for any safety issues and possible new concomitant medications the subject may have started taking. In addition, subjects are to ask if they have had any new warts develop since the last in office visit.

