### **3.10.2.3 Complete Clearance in Subjects With a Single Wart at Baseline**

Proportion of subjects with a single wart at baseline whose wart is Clear (PWA=0) will be summarized descriptively by treatment cycle, analysis visit, and treatment group.

Treatment cycle start date can vary from subject to subject. Subjects with a single Wart in the beginning of treatment cycle and without a Wart assessment at the timepoint analyzed are assigned non-clearance.

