## APPENDIX A: ASSIGNMENT TO ANALYSIS VISIT

Due to the possibility of deviation from the protocol schedule as well as to incorporate data from unscheduled and/or early termination visits, analysis visits are defined below based on Treatment Period Study Day for each treatment cycle. These analysis visits are based on the nominal, scheduled visits in the protocol and treatment cycle. Analysis visit will be used in analyses performed by or on specific visit as well as for the identifiers on data listings. Both nominal visits as collected on the CRF and analysis visits will be retained in the SAS ADaM datasets.

Analysis Visits Within Each Treatment Cycle:

Analysis Visit	Treatment Period Study Day Range	Target Treatment Period Study Day
Px V1	1	1
Px V2	2 - 22	15
Px V3	23 - 36	29
Px V4	37 - 51	43
Px V5	52 - 81	60
Px V6	82 - 127	102
Px V7	128 - 163	144
EOS (End of Study) Visit	$\geq 164$	182

Note: P indicates Treatment Period (Treatment Cycle), x indicates Treatment Period Number (Either 1 or 2 or 3), and V indicates Visit. There is only one EOS visit for all subjects.

In the event that more than one observation falls into the same study day range, the value closest to the “target day” is selected. If there’s a tie in the absolute distance from the target day, the observation with the greater cycle day is selected.

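### Clearance is scored as not clear at phone-call windows where no PWA is due, and the EOS window's cycle-day range conflicts with its own note

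*SAP*

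**What the plan says.** SAP 3.10 defines the primary efficacy endpoint as the proportion of subjects with complete clearance "of all identified warts at each analysis visit window by treatment group and treatment cycle". SAP 3.10.1 takes its visits from period study day through Appendix A and adds the missing-data rule: "Any identified common wart for a subject that has missing PWA data will be treated as not clear". An observed-data sensitivity analysis is planned. SAP 3.10.2.3 applies the same approach to subjects with a single wart: those "without a Wart assessment at the timepoint analyzed are assigned non-clearance".

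The assessment schedule is sparser than the windows. Protocol 9.2 has warts "assessed using the PWA at the following time-points: Day 1, Day 29, Day 60 and Day 182". SAP Table 2 makes the other visits a "phone contact with the subject on Day 15, Day 43, Day 102 and Day 144".

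In SAP Appendix A, "analysis visits are defined below based on Treatment Period Study Day for each treatment cycle", and the EOS row is period day 164 or later with target 182. The note beneath the table says "There is only one EOS visit for all subjects". "In the event that more than one observation falls into the same study day range", the observation nearest the target day is kept.

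Protocol 14.3 words the primary efficacy analysis as clearance at *any* scheduled visit. SAP 3.14, which lists changes from the protocol, mentions only the change of analysis population.

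**The concern.** There are three connected problems.

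1. The missing-data rule covers every window, including those in which nobody is due to be examined. Some rows of the primary and single-wart tables would then report non-clearance only because no assessment was planned.
2. EOS is a study-level visit by the note but a cycle-level window by the range. On the range, a cycle started late in the study has no EOS record, its EOS row is scored not clear, and its end-of-study PWA is filed under an earlier visit. Subjects who entered clear and later needed treatment are the most exposed, and efficacy in recurrent or new warts is a stated secondary objective. Two programmers could build different EOS rows from this text.
3. The endpoint moved from any visit to each window without being recorded. If the protocol's wording means clear at least once, an unassessed phone visit does no harm under the missing-data rule. Under the per-window wording it produces zeros.

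**Working it through.** **Inputs.** PWA days 1, 29, 60 and 182 (Protocol 9.2), with visit windows of +3 days, or +2 days at Day 182 (Table 2). Appendix A ranges in cycle days: V1 1, V2 2–22, V3 23–36, V4 37–51, V5 52–81, V6 82–127, V7 128–163, EOS ≥164. Cycle starts up to Day 122 (SAP 3.3). Period study day counts from the first dose of the cycle (SAP 3.3).

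**The plan's own figure.** SAP 3.13 expects 200 prior-active subjects and 26% clear: 200 × (1 − 0.26) = 148, as stated. The remainder is 200 − 148 = 52.

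**Windows with a PWA due.** Within a cycle, the scheduled PWAs fall on cycle days 29–32 (V3) and 60–63 (V5). For a cycle started on Day 1, Days 182–184 fall in EOS. No PWA is scheduled at the target day of V2, V4, V6 or V7. That is 4 of 8 windows, or 4 of the 7 after baseline.

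**Where the end-of-study PWA goes on the cycle-day range.** Cycle day = study day − start day + 1.

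| Window | Start days, visit on Day 182 | Start days, visit on Day 184 |
|---|---|---|
| EOS | 1–19 | 1–21 |
| V7 | 20–55 | 22–57 |
| V6 | 56–101 | 58–103 |
| V5 | 102–122 | 104–122 |

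Boundary check for Day 182: start 19 gives 182 − 19 + 1 = 164, start 55 gives 128, start 101 gives 82, and start 122 gives 61. These are ranges of start days, not shares of subjects. The visit never falls in V2 or V4.

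**Subjects who enter clear.** Their first scheduled call is Day 42 (+7) and the second is Day 84 (+7) (SAP Table 3). A start on Day 42–49 puts Day 182 at cycle day 141–134 (V7). A start on Day 84–91 puts it at 99–92 (V6). A wart found at a scheduled call therefore cannot start a cycle that reaches EOS. Only a self-reported wart treated by Day 19 (Day 21 for a Day 184 visit) can.

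**Competition within V5, visit on Day 182.** An on-schedule V5 PWA falls on study day start + 59 to start + 62, at 0–3 days from target 60. The Day 182 PWA is 123 − start days from target: 21 for start 102 and 4 for start 119. For starts on Day 102–119 the V5 PWA comes first and is nearer, so the Day 182 PWA is not selected. For starts on Day 120–122 the two visits can coincide, and then nothing is lost.

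**Retreated subjects.** If cycle 2 starts on Day 60–63, Day 182 is cycle-2 day 123–120 (V6) but cycle-1 day 182 (EOS). SAP 3.3 and 3.4 do not say which cycle owns that assessment.

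**Last start day.** SAP 3.3 says Day 122; SAP Table 3 footnote 2 says Day 102. These must be reconciled. With 102, only a Day 102 start would be filed under V5 for a Day 182 visit, and the rest of that map is unchanged.

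**The case against.** Missing data ordinarily means due but not obtained, and Table 2 shows that nothing is due at a phone call. Appendix A says its windows also serve listings and take in unscheduled and early-termination visits, which explains why V2, V4, V6 and V7 exist. Every row except EOS carries the cycle prefix, and the note supports a single study-level EOS; on that reading nothing is misfiled. A 0% row at a phone visit would be noticed at once, and the observed-data analysis would show it empty. Elsewhere, SAP 3.10.2.2 uses only non-missing PWA, SAP 3.10.2.4 is a Kaplan-Meier analysis by cycle, and SAP 3.10.2.1 reports the proportion clear at the end of the study. The figure of 52 is also soft, because 26% is a rate of warts, not subjects.

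Much of this is fair on intent and weight. It does not settle what is written. SAP 3.10.2.3 assigns non-clearance to anyone unassessed at the time point. SAP 3.10.2.2 shows that the authors stated a restriction where they wanted one. SAP 3.4, SAP 3.10.1 and the Appendix A column heading all put visits on the cycle clock. The observed-data analysis removes imputed zeros but uses the same windows, so it does not return a Day 182 PWA to EOS. The limit on the 52 stands.

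**Conclusion.** The concern holds. As written, V2 and V4 show 0% clearance in every cycle, and V6 and V7 do so for cycles started on Day 1 without retreatment, except where an unscheduled or early-termination PWA falls there. On the stated EOS range, first cycles started after Day 19 (Day 21 for a Day 184 visit) have no EOS record. Subjects first treated on Day 1 and later retreated lose theirs only if the Day 182 PWA is counted on the later cycle's clock.

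Most treated subjects should escape the EOS problem, because subjects with warts at entry start treatment at once. The plan's figures put at most 52 of 200 prior-active subjects as clear at entry, reading a wart rate as a subject rate. How many of these, or of the vehicle subjects, later start a cycle is not in the documents, so no effect on the reported percentages is estimated. No test or error rate is involved. Even so, the rows belong to the named primary efficacy table and should be corrected before it is produced.

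**What to change.** - Define EOS by study day or nominal visit, and report it once at study level, outside the cycle windows.
- Limit the primary and single-wart clearance tables to post-baseline windows with a scheduled PWA: V3 and V5 in each cycle, plus study-level EOS. Apply missing = not clear only there.
- Record in SAP 3.14 the move from any scheduled visit to each analysis window, and state which meaning is used.

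The cost is wording and programming in SAP 3.10.1, 3.10.2.3, 3.14 and Appendix A. Nominal visits are already kept in the datasets, so no new data are needed. The drawback is that unscheduled and early-termination PWAs in V2, V4, V6 or V7 would appear only in listings and the observed-data analysis. Those windows cover 21 + 15 + 46 + 36 = 118 of the 162 cycle days from 2 to 163, so the SAP should state this loss. A lighter alternative keeps those rows on observed data only, but they would then rest on the few subjects seen off schedule.
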